[name]

Official Title: Use of protamine for heparin reversal after catheter ablation of atrial fibrillation

NCT Number: NCT03140631

Date of Approval: 10/18/2017

Title: Use of protamine for heparin reversal after catheter ablation of atrial fibrillation: A randomized trial

Introduction:

Catheter based ablation is a well-established and highly effective treatment for atrial fibrillation and the use of such therapies are increasing [1, 2]. To mitigate the risk of intraprocedural thromboembolism, intravenous heparin is administered to maintain an activated clotting time(ACT) of >300s [3]. At the completion of a procedure it can take several hours for a patient's ACT to normalize and for sheaths to be removed. However prolonged sheath presence may increase the risk of vascular complications which may not be infrequent (up to 6-9%) and can be associated with morbidity and increase in costs. A common strategy is to administer protamine sulfate to rapidly (within 5min) neutralize the effect of heparin to expedite sheath removal and patient ambulation and length of stay. Both of these approaches are standard of care practices, have been widely used and reported as case series. However, despite wide-spread clinical use, these two approaches have not been evaluated in a prospective, randomized manner. The objective of this study is to evaluate the safety, efficacy and efficiency of rapid anticoagulation reversal with protamine sulfate versus routine ACT monitoring in patients undergoing catheter based ablation of atrial fibrillation.

Background:

Protamine Sulfate:

Protamine has been used to facilitate in-laboratory sheath removal after percutaneous coronary interventions for over twenty years [4] and has been shown to decrease time to ambulation without increased rates of thrombosis or access site complications[5]. Protamine reversal of heparin anticoagulation also has an established track record in patients undergoing peripheral endovascular intervention[6] and is used commonly after cardiopulmonary bypass as well[7]. Protamine sulfate is a highly basic protein that forms stable compounds with acidic heparin to neutralize the anticoagulation effects and is itself not a procoagulant agent[8]. While randomized trials and larger studies are needed, it has not been shown to significantly increase rates of post-procedure thrombosis [4-7, 9, 10]. Further catheter ablation for atrial fibrillation is performed via venous approach and under **uninterrupted anticoagulation**.

Protamine can cause hypersensitivity reactions leading to rash, hypotension, pulmonary edema, and cardiovascular collapse[8]. Chilukuri et al reported on 242 patients undergoing atrial fibrillation ablation who received protamine for sheath removal and reported adverse reactions to protamine in 1.2% of cases which was similar to prior reports of protamine exposure[11].

Vascular Complications after ablation procedures:

Vascular access for ablation procedures can be complicated often requiring multiple venous access sites and long procedure and patient flat-time. These factors are known to be associated with increased rates of vascular complications [12, 13]. Patient specific factors, such as the use of antiplatelet agents and female gender, can increase the risk as well[14]. Newer technologies such as cryotherapy techniques require placement of large diameter sheaths which may raise the risk of vascular access complications [12]. Bleeding and thromboembolic complications after atrial fibrillation ablations are common and have been on the rise, predominantly due to increased vascular access complications [15]. Current guidelines recommend intraprocedural heparin be administered prior to or immediately following transeptal puncture [3] and this periprocedural anticoagulation may contribute to the rate of vascular access site complications [9]. A large study of Medicare beneficiaries reported the incidence of any vascular complication from AF ablation to be 6.9%[15] in 2006 up from 5.4% in 2001[15].

The rate of occult femoral DVT after placement of multiple venous sheaths has been reported in several series and ranges from approximately 5-18%[12, 13, 16]. Davutoglu et al performed serial vascular ultrasounds in 27 patients undergoing electrophysiology studies and found that post-procedural occult femoral DVTs were present in 62.5% of patients [13]. This rate was decreased to 18% with the use of prophylactic low-molecular weight heparin (p=0.02). Nearly all cases resolved after treatment with warfarin. Chen et al[16] examined 54 patients undergoing electrophysiology study (EPS) and/or RFA ablation, with routine heparinization only administered for left-sided ablation procedures, pre- and post-procedural vascular ultrasounds were performed. There was a 17.6% incidence of non-occlusive DVT in patients who underwent placement of multiple sheaths, this incidence was not significantly affected by the use of intraprocedural heparin. In these series, the DVTs were asymptomatic and demonstrated regression or resolution on follow-up imaging. In our series DVT has not been a concern. Further catheter ablation for atrial fibrillation is performed via venous approach and under **uninterrupted anticoagulation.**

Clinical diagnosis of hematoma formation immediately after EPS or ablation was reported by Dalsgaard et al[17]. The rate of hematoma formation immediately after EP procedures was 10%, with 27% of patients reporting a significant hematoma after 14 days. The rate of hematoma formation was higher in patients undergoing atrial fibrillation/flutter procedures than in those undergoing VT/VES procedures both immediately after the procedure (19% vs 5%) and at 14 days (31%vs 11%). Due to insidious nature of venous bleeding, the prevalence of hematomas can be higher after venous access. A critical factor on the true prevalence of hematomas reported in the literature is the rigor with which hematomas were assessed and reported explain the wide variation in prior reports.

Protamine administration after ablation procedures:

Several non-randomized, single center studies have reported on the safety and efficacy of protamine use in patients undergoing electrophysiology studies and ablations (Table 1). Patel et al performed a retrospective cohort evaluation comparing 116 patients who received protamine sulfate against 42 who did not [2]. The majority of patients (138/158) had undergone an atrial ablation while only a minority (11/158) underwent ventricular ablation procedures. They reported no significant differences in bleeding or thromboembolic events between the two groups. Routine imaging including vascular ultrasound was not utilized and bleeding events were defined as blood loss requiring transfusion, hematoma requiring intervention, or intracranial hemorrhage. Using these clinical definitions, the authors concluded that a randomized clinical trial of 1606 patients would be necessary to fully evaluate the use of protamine.

Conte et al reported on 54 consecutive patients receiving protamine after cryoballoon ablation of atrial fibrillation compared to 53 historic controls who did not[9]. The use of protamine was associated with less intensive care monitoring time as well as fewer vascular complications (11% vs 0%, p<0.01), primarily fewer minor groin hematomas treated conservatively). Gurses et al performed a retrospective study examining protamine use after the use of cryoballoon therapy for AF[10]. In this larger study of 380 patients the authors concluded that routine use of protamine was associated with a shorter time to sheath removal, faster mobilization, shorter hospital stay as well as fewer vascular access complications (hematoma/pseudoaneurysm or arteriovenous fistula, 6.3% vs 1.0%, p=0.011) without an increase in thrombotic events (TIA, CVA, DVT).

Frankel Cardiovascular Center Experience:

The University of Michigan is a high-volume ablation center with particular expertise in treating atrial fibrillation using both radiofrequency and cryoballoon ablation techniques. The Cardiac Arrhythmia Service performs approximately 1,100 ablation procedures per year including nearly 700 procedures for atrial arrhythmias primarily for atrial fibrillation. Protamine has not been incorporated into routine lab protocols for post-procedure care and is administered based on operator preference. Owing to the very low risk of significant complications specifically embolic events (<0.5%) over the years with the current approach, protamine has not been routinely used unless there is a clinical need. However, published case series suggest that protamine can safely be utilized to expedite vascular hemostasis. Therefore there is both a scientific and clinical need to determine whether each approach is comparable and whether one is superior to the other. There already is sufficient body of literature from this and other institutions demonstrating the utility of either approach.

A brief audit of recent procedures shows that in cases where rapid reversal with protamine is not used, the average time from patient arrival to the post-procedure unit to sheath removal is 204 ± 47 minutes; this delay is nearly entirely attributed to the time required for the critical

decrease in ACT to allow safe sheath removal. This prolongs patient time to ambulation and may contribute to outcomes.

Summary:

The use of protamine sulfate for rapid heparin neutralization and early sheath removal after catheter based therapies has been used with good results in a variety of clinical settings. However, much of the safety and efficacy data are derived from small, non-randomized, and retrospective series and have been performed in patients undergoing coronary and vascular interventions involving single vessel access. Ablation procedures involve the use of more vascular access, larger diameter sheaths, prolonged procedure times, more intensive anticoagulation protocols, and carries the risk of ablation lesion related thrombosis[3] which limits the applicability of the existing data. The few studies examining the use of protamine for atrial ablation have all been small, non-randomized cohorts but have suggested improved vascular access outcomes as well as decreased time to patient ambulation. Randomized prospective data are needed to corroborate these findings.

Objective and Hypothesis:

The objective of this study is to evaluate the safety, efficacy and efficiency of rapid anticoagulation reversal with protamine sulfate vs routine ACT monitoring in patients undergoing catheter based ablation of atrial fibrillation. We hypothesize that the routine use of protamine sulfate will facilitate early sheath removal, early ambulation, and improve patient comfort with a significant decrease in the rate of vascular access site complications and time to ambulation. The primary study endpoint will be the 30-day occurrence of vascular access site complications (major or minor groin bleeding including hematoma formation, aneurysm, pseudoaneurysm, AV fistula, deep venous thrombosis).

Methods and Study Protocol:

Study design:

Single center, controlled, prospective, superiority, parallel-group, open-label, randomized clinical trial.

Study Site:

Electrophysiology laboratories and outpatient clinics at the University of Michigan Health System Frankel Cardiovascular Center.

Study Population and Enrollment:

Adult patients undergoing clinically indicated RFA or cryoballoon ablation for atrial fibrillation or atrial flutter (left atrial) will be prospectively enrolled. Consideration for enrollment and obtainment of patient consent will be performed in the pre-operative setting in the cardiac procedures unit prior to the ablation procedure. Consent will be obtained by the study coordinator using both verbal and written study information.

Inclusion Criteria:

- Patient's referred for RFA or cryoablation for atrial fibrillation or atrial flutter (left atrial).
- Age ≥ 18 year
- Patients who are mentally and linguistically able to understand the aim of the trial, comply with the trial protocol, verbally acknowledge the risks, benefits, and alternatives in this trial.

Exclusion Criteria:

- Previous intolerance or allergy to heparin products.
- Current or prior administration of protamine products
-
- History of femoral access site complications including hematoma, AV fistula, pseudoaneurysm, aneurysm.
- Known lower extremity venous thrombosis.
- Coagulopathy or blood dyscrasias.
- Active malignancy.
- Thrombocytosis (platelet count $>600k/\mu l$) or thrombocytopenia (platelet count $<100k/\mu l$)
- Planned use of vascular closure device

Randomization:

A randomization will be performed in a block manner. Patients will be randomized to one of two parallel treatment strategies, namely protamine sulfate group or standard sheath removal group (control).

Pre-Procedural and Procedural Management:

A pre-procedure groin and lower extremity examination will be documented. Patients on warfarin will continue on uninterrupted therapeutic anticoagulation through the procedure. Patients on direct-acting oral anticoagulants will discontinue the medication one dose prior to their procedure and will resume taking it after hemostasis has been achieved post-procedurally. Prior to heparin administration, ACT will be checked as a target for anticoagulation reversal prior to sheath removal.

Patients will undergo routine pre-procedural assessment and selection of radio frequency ablation (RFA) or cryoablation at the discretion of the treating physician. Procedural endpoints and ablation targets (i.e. pulmonary vein isolation, targeting of complex atrial fractionated electrograms, linear ablation lines, et cetera) are not specified by this protocol and will be performed at the discretion of the treating physician and in accordance with the ablation method selected. An intraprocedural targeted ACT of 300-400s is recommended in accordance with the current guidelines.

Vascular access will be obtained using fluoroscopic and ultrasound guidance using the standard modified-Seldinger technique. Patients undergoing RFA will have right femoral vein access with the use of two 8.5F long-sheaths and one 8F short-sheath. Patients undergoing cryoballoon ablation will have right or both femoral vein access with the use of a 14F long-sheath and 8F short sheath.

Postprocedural management:

Patients randomized to the intervention group will receive a test dose of protamine sulfate 0.5 mg with close monitoring for adverse reactions. If no reactions occur after 5 minutes patients will continue with the intervention group or otherwise undergo routine sheath removal. Protamine sulfate dose will be determined by the amount of heparin received during the last hour of the procedure (1mg of protamine per 100 units of heparin, maximum of 50 mg) and will be administered over 5 minutes, with close hemodynamic monitoring during and after the infusion. ACT levels will then be monitored with a goal ACT of <200s or return to preprocedural baseline.

The non-intervention group will undergo routine ACT measurements beginning 90min after the cessation of the procedure with a goal ACT<200s or return to preprocedural baseline before sheath removal.

Manual compression using the standard technique by professional staff, will be applied until hemostasis is achieved, followed by a 6-hour period of flat time before ambulation. Patients will be monitored overnight for post-procedural observation which is the current standard of care in our laboratory.

Immediately after the sheath removal and the morning after the procedure, detailed examination of both groins will be performed for signs of bleeding, hematoma, aneurysm, or fistula as standard of care and will be carefully documented. Patients with signs or symptoms of vascular complications will undergo duplex venous ultrasound as usual standard of care. In addition Hemoglobin and hematocrit levels will be documented before and the morning after the procedure as per routine clinical care protocol.

Post-procedural anticoagulation will be administered for at least two months per national guideline recommendations; choice of anticoagulation and duration beyond two months will be at the discretion of the treating physician.

Data Collection and Analysis:

Baseline demographic, clinical, procedural and ultrasound data will be collected. Patients will be monitored overnight post procedure (18-24 hours) with routine assessment of clinical access site, neurologic checks, and patient comfort scores. Patients will have one-week phone follow up and three month clinical visits to assess thromboembolic and bleeding events as well as procedural outcomes. Data collection formed is shown (see attached form).

Vascular ultrasound will be obtained if clinically indicated as described above. Results will be interpreted by two independent, qualified readers to ensure standardization and accuracy. Discrepant interpretations will be jointly reviewed for agreement.

Study endpoints:

The primary study outcome will be total time to ambulation; the start time (time zero) will be procedural termination. Secondary endpoints will include the 90-day occurrence of vascular access site complications defined as hematoma formation, aneurysm, pseudoaneurysm, arteriovenous fistula formation, access-site related major bleeding (defined as BARC type 3a or 5[18]), or procedural intervention for access complications (surgical repair, thrombin injection, et cetera). Additional exploratory endpoints will be the time to achieve hemostasis, duration of manual compression, need for repeat manual compressions, the total number of re-bleeding events, patient reported hematoma on 7 day phone call, and patient reported groin pain at discharge, 7 day phone call, and follow up appointment.

Safety endpoints:

Safety endpoints will be thrombotic events defined as stroke or transient ischemic attack, deep vein thrombosis, pulmonary embolism, lower extremity thromboembolic events, acute myocardial infarction, or death. There is no plan for an interim analysis.

Statistical Analysis:

Based on preexisting studies and an audit of quality data from our own laboratory, we anticipate a baseline time-to-ambulation of 360 ± 180 min with a reduction to 270 min with the use of protamine. We estimate that the enrollment of 150 patients would provide 80% power to detect the anticipated difference in the primary outcome at the 5% two-sided level of significance, assuming a 10% loss to follow up. Prespecified sub-groups for secondary analysis include sex, age, clinical comorbidites (BMI, diabetes, CHF), ablation method, use of antiplatelet medications, prior ablation procedure, prior coronary angiography or intervention.

Data will be reported as means and standard deviations or as absolute values and percentages where appropriate. The Chi Square and Fisher's exact test will be used to compare categorical

variables. Unpaired or paired Student's t-test or the Mann-Whitney test will be used as appropriate. A P value less than 0.05 will be considered statistically significant.

Clinical Significance:

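### The protocol names two different primary endpoints: 30-day vascular complications (Objective and Hypothesis) and time to ambulation (Study endpoints); only the second is powered

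*Combined protocol and SAP*

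**What the plan says.** The Objective and Hypothesis section says: "The primary study endpoint will be the 30-day occurrence of vascular access site complications". Its composite covers major or minor groin bleeding including hematoma, aneurysm, pseudoaneurysm, AV fistula and deep venous thrombosis. The hypothesis just before it expects "a significant decrease in the rate of vascular access site complications and time to ambulation", so it names both outcomes and ranks neither.

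The Study endpoints section says: "The primary study outcome will be total time to ambulation; the start time (time zero) will be procedural termination". It continues: "Secondary endpoints will include the 90-day occurrence of vascular access site complications". The components there are hematoma, aneurysm, pseudoaneurysm, AV fistula, access-site major bleeding of BARC type 3a or 5, and procedural intervention for an access complication. Deep vein thrombosis appears under Safety endpoints instead: "Safety endpoints will be thrombotic events defined as stroke or transient ischemic attack, deep vein thrombosis, pulmonary embolism".

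The only sample-size statement, in Statistical Analysis, uses 360 ± 180 min falling to 270 min and reads: "We estimate that the enrollment of 150 patients would provide 80% power to detect the anticipated difference in the primary outcome". The same section sets P<0.05 as the significance threshold. Study design describes the trial as "Single center, controlled, prospective, superiority, parallel-group, open-label, randomized clinical trial".

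**The concern.** A superiority trial needs one identified primary endpoint, fixed before the data are seen, or an explicit co-primary or hierarchical scheme. This protocol has two sentences that each name a different primary, and no co-primary definition, testing order or division of alpha.

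Three things are at stake:

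- **Selective reporting.** Treatment is open-label and every test is at P<0.05. Whichever endpoint succeeds could be presented as the protocol's primary.
- **Classification of patients.** The complication endpoint itself differs between the two sections. A minor groin bleed without hematoma, a deep vein thrombosis or an event on day 45 counts under one definition and not under the other.
- **Power.** The stated 80% applies to minutes to ambulation. If the Objective section governed, the primary endpoint would have no documented power.

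**Working it through.** **1. The two sections side by side**

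| Item | Objective and Hypothesis | Study endpoints / Safety endpoints |
|---|---|---|
| Primary | Vascular access complications | Time to ambulation |
| Status of vascular complications | Primary | Secondary |
| Window | 30 days | 90 days |
| Bleeding | Major or minor groin bleeding, including hematoma | Hematoma; other bleeding only if BARC 3a or 5 |
| Deep vein thrombosis | In the composite | Safety endpoint |
| Procedural intervention | Not listed | In the composite |

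Both are operative text; neither belongs to an amendment log or a redacted passage.

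**2. The plan's own sample size (time to ambulation)**

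Inputs from Statistical Analysis: means 360 and 270 min, SD 180, two-sided 5%, 80% power, 10% loss. The allocation ratio is not stated; 1:1 is assumed.

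- Standardised difference: (360 − 270)/180 = 0.5.
- Two-sample t-test: 63.8, so 64 per arm and 128 in total.
- Allowing for loss: 128/0.9 = 142.2, so 143 enrolled.
- Planned: 150 enrolled; 150 × 0.9 = 135 evaluable, or 67 per arm rounded down. Power at 67 per arm is 0.819.

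The 150 is slightly more than needed and is not itself a fault.

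**3. Power if the complication composite were primary**

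No rate is given for this purpose, so these are illustrations using rates cited in the background. Power is exact, by enumerating all outcomes at 67 per arm. Statistical Analysis names both Fisher's exact and chi-square tests without saying which applies, so both are shown.

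| Control vs protamine | Source | Fisher | Chi-square |
|---|---|---|---|
| 6.3% vs 1.1% | Table 1, larger cryoballoon series | 14% | 35% |
| 6.9% vs 3.45% | Medicare study rate; halving assumed | 6% | 14% |
| 19% vs 9.5% | Immediate hematoma rate, AF/flutter procedures; halving assumed | 27% | 35% |
| 31% vs 15.5% | 14-day hematoma rate, AF/flutter procedures; halving assumed | 50% | 57% |
| 11% vs 0% | Background text, smaller cryoballoon series | 76% | 95% |

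For 80% power, with p̄ = (p₁ + p₂)/2, the pooled normal approximation is

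n per arm = [1.96·√(2p̄(1−p̄)) + 0.842·√(p₁(1−p₁) + p₂(1−p₂))]² / (p₁ − p₂)².

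Enrolment after 10% loss is 2n/0.9:

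- 6.3% vs 1.1%: 206 per arm, 412/0.9 = 457.8, so 458.
- 6.9% vs 3.45%: 647 per arm, 1294/0.9 = 1437.8, so 1438.
- 11% vs 0%: 67 per arm, 134/0.9 = 148.9, so 149.

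The last case lands close to 150, so the number 150 alone does not show which endpoint was sized. The wording of Statistical Analysis does: it gives minutes. The 11% vs 0% input is also insecure, because Table 1 prints that study as 6/54 (0%) and 11/53 (11%), whereas 6/54 = 11.1% and 11/53 = 20.8%.

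The only complication-based sample size in the document is the 1606 patients attributed to an earlier retrospective cohort, which used a narrower bleeding definition.

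**The case against.** The strongest reply is that Study endpoints plainly governs. It sits in the operative methods, it calls time to ambulation primary, and the sample-size paragraph does so again by sizing the primary outcome in minutes. On this reading the Objective sentence is leftover text and no competent analyst would be misled. The inference is probably right, but the document does not state it. The Objective section is where a reader first looks for the primary endpoint, and its sentence remains available to cite.

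Four narrower points stand as caveats:

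- The power figures for complications are secondary. The contradiction is textual and would hold whatever the rates. The cited studies define events differently from the 30-day composite, so the table does not bound its power.
- The 82% for time to ambulation is conditional on the plan's inputs. Postprocedural management sets a 6-hour (360 min) flat period after hemostasis before ambulation, which does not fit means of 360 and 270 min counted from procedural termination. Those passages need reconciling separately.
- Neither window is well covered by scheduled contacts. Data Collection and Analysis lists a one-week call and a three-month visit with nothing between. A 90-day window ends near a visit and a 30-day window does not, but events after the first week rest on records or recall under both.
- The data collection form mentioned in the protocol was not among the text available, though it is unlikely to settle which endpoint is primary.

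**Conclusion.** The concern holds. Two current sections name different primary endpoints, and the complication endpoint differs between them in rank, window and components. Power is documented for time to ambulation only: about 82% at 67 per arm, assuming 1:1 allocation, 10% loss and the stated means and SD. For the 30-day composite, power is undocumented, not shown to be low; the illustrations run from 6% to 95% depending on the assumed rates and the test. The main harm is that either endpoint could be reported as the protocol's primary in an open-label trial. This must be fixed.

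**What to change.** The sponsor should first confirm which endpoint is intended. If it is time to ambulation, as the sample-size text indicates:

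1. Replace the primary-endpoint sentence in Objective and Hypothesis with, for example: *Time to ambulation, counted from procedural termination, is the sole primary endpoint and is tested at the two-sided 5% level. Vascular access complications are secondary and are defined under Study endpoints.*
2. Use one window and one component list for vascular complications in both sections. The 90-day version ends near the scheduled three-month visit.
3. Count deep vein thrombosis in one place, either in the composite or under safety.

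This is a wording amendment; it needs no more patients, visits or procedures. If the sponsor instead intended 30-day complications as primary, the cost is larger: a sample-size justification for that composite would be needed, and possibly a contact at 30 days.

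### The plan names two different primary endpoints and sizes only one of them; the complication endpoint is also assessed without stated masking

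*Combined protocol and SAP*

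**What the plan says.** Objective and Hypothesis states: "The primary study endpoint will be the 30-day occurrence of vascular access site complications (major or minor groin bleeding including hematoma formation". The list continues with aneurysm, pseudoaneurysm, AV fistula and DVT.

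Study endpoints states: "The primary study outcome will be total time to ambulation; the start time (time zero) will be procedural termination". It then says: "Secondary endpoints will include the 90-day occurrence of vascular access site complications defined as hematoma formation, aneurysm, pseudoaneurysm, arteriovenous fistula formation". BARC 3a or 5 access-site bleeding and procedural intervention complete that composite. DVT appears only under Safety endpoints.

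The sample-size statement in Statistical Analysis reads: "We estimate that the enrollment of 150 patients would provide 80% power to detect the anticipated difference in the primary outcome". Its inputs are times in minutes.

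On assessment, Study design describes the trial as "Single center, controlled, prospective, superiority, parallel-group, open-label, randomized clinical trial". Postprocedural management says that, right after sheath removal and the next morning, "detailed examination of both groins will be performed for signs of bleeding, hematoma, aneurysm, or fistula as standard of care". Duplex follows signs or symptoms. On the scans, Data Collection and Analysis says: "Results will be interpreted by two independent, qualified readers to ensure standardization and accuracy". Discrepancies go to joint review. Planned follow-up after the overnight stay is a call at one week and a visit at three months. A data form is said to be attached, but it is not in the supplied text.

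**The concern.** Both endpoint statements are current text, and neither defers to the other. They differ in what is primary, in the complication window, and in whether minor bleeding and DVT count. A trial that shortens time to ambulation without a significant fall in complications would succeed under one and fail under the other. A reader of the results could not tell from the plan which claim was confirmatory.

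The second issue is how complications are called. The arms are easy to tell apart: one gets a protamine test dose and infusion, the other waits for ACT checks that start at 90 minutes. Hematoma has no size or severity threshold in the supplied text; the BARC grade applies only to major bleeding. The background section itself attributes the wide spread of published hematoma rates to how rigorously they were assessed. Knowledge of the arm could therefore affect which borderline swellings are recorded. Under Study endpoints that touches a secondary composite; under the Objective it would touch the primary.

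**Working it through.** **1. The two versions side by side**

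| | Objective and Hypothesis | Study endpoints and Safety endpoints |
|---|---|---|
| Primary | Access-site complications | Time to ambulation |
| Complication window | 30 days | 90 days |
| Minor groin bleeding | Named | Not named |
| Procedural intervention | Not named | Named |
| DVT | In the composite | Safety only |
| Sample size | None | 150 |
| Matching scheduled contact | None at 30 days | Three-month visit |

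**2. The plan's own figure.** Statistical Analysis gives a difference of 360 − 270 = 90 min, SD 180, two-sided 5%, 80% power and 10% loss.

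- Normal approximation: n per arm = 2 × (1.96 + 0.842)² × (180/90)² = 62.8, so 63. The total is 126, and 126/0.9 = 140.
- t-based: 64 per arm, 128 in total, 143 after loss.
- Mann-Whitney, which the plan also lists (efficiency 0.955): 66 or 68 per arm, 147 or 152 in total after loss.
- In reverse: 150 × 0.9 = 135, or 67.5 per arm. The standard error is 180 × √(2/67.5) = 30.98, and Φ(90/30.98 − 1.96) = 82.8%.

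The plan does not name its formula, but 150 is consistent with its stated inputs and belongs to time to ambulation. The inputs are taken as given here. Whether mean times of 360 and 270 min fit the six-hour flat period in Postprocedural management is a separate matter to reconcile.

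**3. If complications were primary.** The plan gives no expected rates and no allocation ratio. Assumed: 1:1, 67 evaluable per arm, and the larger cryoballoon cohort's rates in Table 1, 6.3% without and 1.1% with protamine (the text says 1.0%).

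- Pooled rate: (0.063 + 0.011)/2 = 0.037.
- SE under the null: √(2 × 0.037 × 0.963/67) = 0.0326.
- SE under the alternative: √((0.063 × 0.937 + 0.011 × 0.989)/67) = 0.0323.
- Power = Φ((0.052 − 1.96 × 0.0326)/0.0323) = Φ(−0.369) = about 36%.
- Fisher's exact test, summing over both binomial distributions: about 14%.
- For 80% power, the same approximation needs 206 per arm, 412 evaluable, and 412/0.9 = 458 enrolled.

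Range, by the same approximation at 67 per arm:

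- 6.9% (the Medicare figure) halved: 14%.
- 19% (the immediate hematoma rate in AF/flutter patients) halved: 35%.
- 11% vs 0% (the smaller cryoballoon cohort, computed at 0.1%): 79%, rough so close to zero. That cohort's counts in Table 1 do not match its percentages.

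The halvings are assumptions.

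**4. What assessment bias could do.** The documents give no recording error, so this is illustration only. Assume no true effect, 75 per arm, all control events recorded, and a share u of protamine-arm events unrecorded. The recorded protamine rate is then r(1 − u). The chance of a two-sided Fisher p < 0.05 is:

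| True rate r | u = 0 | u = 20% | u = 50% |
|---|---|---|---|
| 6.3% | 1.9% | 2.3% | 5.9% |
| 19% | 3.0% | 6.1% | 30.4% |

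For example, at r = 19% and u = 50%, the recorded rates are 19% and 9.5%.

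**The case against.** The strongest reply on the endpoint is that the plan can be read only one way. The section devoted to endpoints and the only sample size agree on time to ambulation, so the sentence in the Objective looks like a leftover. That is probably how the plan was meant, and it settles which way to amend. It does not remove the conflict: nothing in the text says which statement governs.

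On bias, several replies stand. An open-label design is disclosed. There is a documented pre-procedure groin examination, two examinations at fixed times, overnight access-site checks, hemoglobin and hematocrit, a three-month visit, and harder components in the composite. The missing form may contain a hematoma definition. The non-recording fractions above have no source, and mild bias at low rates leaves the error rate below 5%. Independent reading with joint review does standardize scans, but it does not say that the arm is hidden.

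Three stronger readings are tempting, and the documents support none of them.

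- A reader might infer that the complication result will favor protamine falsely. Neither the direction nor the size of any bias is established.
- A reader might put the cited 14-day AF/flutter hematoma rate of 31% into the bias table for a more alarming figure. The background words the 14-day data as patients' reports, not examiners' findings. The plan keeps "patient reported hematoma on 7 day phone call" as a separate exploratory endpoint.
- A reader might infer that occult DVT is being missed improperly. The plan discloses that duplex follows signs or symptoms and makes no claim about occult DVT.

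**Conclusion.** The plan is inconsistent on its primary endpoint and should be corrected. This follows from the text alone and needs no assumption. Its consequence is material but not fixed in size: the enrolled number suits time to ambulation, while power for a complication primary was never planned. That power would be about 36% (normal approximation) or 14% (Fisher) at 6.3% vs 1.1%, and runs from 14% to 79% by normal approximation across the other rates tried.

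The masking point holds as a secondary one. The hematoma component is open to assessment bias of unknown size and direction. Under assumed non-recording the effect runs from negligible (1.9% to 2.3%) to large (3.0% to 30.4%). The absence of a size rule is provisional until the attached form is seen. If time to ambulation is confirmed as primary, the bias point concerns one secondary composite and does not undermine the trial's main comparison.

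**What to change.** 1. Amend the endpoint sentence in Objective and Hypothesis to agree with Study endpoints: time to ambulation as the sole primary, and one complication composite as secondary with one window and one component list. State whether minor bleeding and DVT belong to it. The hypothesis already names both outcomes, so only the endpoint sentence need change.
2. In Data Collection and Analysis, give the two existing readers each scan with the treatment arm removed. State that groin examination and the decision to scan remain open-label.
3. Optional, after checking the attached form: record the largest measured diameter of any groin swelling at the two scheduled examinations and report hematomas by size in each arm. The composite can then be shown with and without small hematomas. The documents give no size figure, so none is proposed.

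The cost is protocol wording, minor handling of images and, if item 3 is adopted, one measurement at examinations already planned. No extra readers, scans or visits are needed. Masked reading does not reach hematomas called at the groin examination, and the diameter would still be measured by someone who may know the arm. Some bias therefore remains and should be acknowledged when the complication result is reported.
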